16.3 Geographic Regions

Table 11 Geographic Regions

Country	Region
Japan	Asia
Korea, Republic of	Asia
Bosnia and Herzegovina	Eastern Europe
Bulgaria	Eastern Europe
Croatia	Eastern Europe
Czech Republic	Eastern Europe
Estonia	Eastern Europe
Hungary	Eastern Europe
Lithuania	Eastern Europe
Poland	Eastern Europe
Romania	Eastern Europe
Russia	Eastern Europe
Serbia	Eastern Europe
Slovakia	Eastern Europe
Ukraine	Eastern Europe
Austria	Western Europe
Belgium	Western Europe
Germany	Western Europe
Greece	Western Europe
Ireland	Western Europe
Italy	Western Europe
Netherlands	Western Europe
Portugal	Western Europe
Spain	Western Europe
Switzerland	Western Europe
United Kingdom	Western Europe
Argentina	ROW
Australia	ROW
Brazil	ROW
Colombia	ROW
Israel	ROW
Lebanon	ROW
Mexico	ROW
New Zealand	ROW
South Africa	ROW

Country	Region
Turkey	ROW
Canada	North America
United States	North America

ROW (Africa/Australia/Latin America/Middle East). Asia (Japan/South Korea)

16.4 UC Medication History or Use Subgroup Identification

The following UC medications/therapies/procedures are recorded on the concomitant medication indication specific form.

- **Immunosuppressant Experienced at Baseline**
 - Rule
 - Yes: At least one of the listed medications is on or before the date of the first dose of study medication in the induction study
 - No: Otherwise
 - **Immunosuppressant Use at MNT Baseline**
 - Rule
 - Yes: At least one of the listed medications is used 6 days prior to the dose of study medication at the Week 12 visit in the induction study
 - No: Otherwise
 - **Anti-TNF Experienced**
 - Recorded in induction study eCRF (Ulcerative Colitis History); Experienced (Yes)/Naïve (No)
 - **Anti-TNF Failure**
 - Rule
 - Yes: At least one of the anti-TNF medications is on or before the date of the first dose of study medication in the induction study and “Inadequate response” or “Loss of response” was the reason for the discontinuation.
 - No: Otherwise
 - **Anti-TNF Failure Times**
 - Rule
 - Naïve: None of the anti-TNF medications is on or before the date of the first dose of study medications in the induction study
 - Experienced without failure: At least one of the anti-TNF medications is on or before the date of the first dose of study medication in the induction study but “Inadequate response” or “Loss of response” is NOT the reason for discontinuation
 - Number of failures: Count (1, 2, or 3 or more): Count the number of unique records on or before the date of the first dose of study medication in the induction study where anti-TNF medication is in the list below and “Inadequate response” or “Loss of response” is the reason for the discontinuation.
 - **Glucocorticoid Use at Baseline**
 - Rule
 - Yes:
 - At least one systemic glucocorticoids in the 6 days prior to the first dose of study medication in the induction study given by “oral” route
- OR

- At least one topical glucocorticoids in the 6 days prior to the first dose of study medication in the induction study given by “oral” route
 - No: Otherwise
 - **Glucocorticoid Use at MNT Baseline**
 - Rule
 - Yes:
 - At least one systemic glucocorticoids in the 6 days prior to the dose of study medication at the Week 12 visit in the induction study given by “oral” route
 - OR
 - At least one topical glucocorticoids in the 6 days prior to the dose of study medication at the Week 12 visit in the induction study given by “oral” route
 - No: Otherwise
 - **Maximum Prior Treatment Experience**
 - Immunosuppressant experienced:
 - Rule
 - Yes: At least one of the listed medications in or before the date of the first dose of study medication in the induction study
 - No: Otherwise
 - Biologic Failure
 - Rule
 - Yes: At least one of the listed medications on or before the date of first dose of study medication in the induction study and “Inadequate response” or “Loss of response” was the reason for the discontinuation.
 - No: Otherwise
 -
 - Systemic glucocorticoid experienced
 - Rule
 - Yes: least one of the systemic glucocorticoids on or before the date of first dose of study medication in the induction study given by “Oral”, “Intravenous”, or “Intramuscular”
 - No: Otherwise
 - Topical glucocorticoid experienced
 - Rule
 - Yes:
 - At least one of the topical glucocorticoids on or before the date of first dose of study medication in the induction study given by “oral” or “rectal” route.
 - OR

- At least one of the systemic glucocorticoids on or before the date of first dose of study medication in the induction study given by “rectal” route.
- OR
- At least one of the following medications on or before the date of first dose of study medication in the induction study regardless of route.
 - PROCTOFOAM
 - PROCTOSEDYL /03159801/”
 - STEROIDS
 - CORTICOSTEROIDS ACTING LOCALLY
 - ENTOCORT ENEMA
 - ENEMAS
 - No: Otherwise
- Amino salicylates experienced
 - Rule
 - Yes: At least one of the listed medications on or before the date of first dose of study medication in the induction study
 - No: Otherwise
 - **5-ASA Use at MNT Baseline**
 - Rule
 - Yes: At least one of the listed medications in the 6 days prior to the dose of study medication at the Week 12 visit in the induction study given by “oral” or “rectal” route
 - No: Otherwise

16.5 Rescue Therapy for Ulcerative Colitis

In order for a medication to be a rescue therapy for UC, it should be reported on the concomitant medication indication specific form.

If the exposure happens in the follow-up period (beginning on the EOT date), then it would not satisfy the criteria, as we are concerned here only about exposure with regards to the estimand, which is during the treatment period.

- **Biologics with immunomodulatory properties**
 - Any exposure after first dose
- **Non-biologics with immunomodulatory properties**
 - **Immunosuppressants**
 - Rule
 - After first dose and up to and including Week 48: any increase from MNT baseline for more than 5 days
 - After Week 48: Any dose above MNT baseline for greater than 1 day
 - MNT baseline
 - Subjects who have at least one dose in the 6 days prior to the dose of study medication at the Week 12 visit in the induction study will be considered to have a MNT baseline dose >0 . The MNT baseline dose to be used for these subjects is the median nonmissing daily dose from these 6 days. Subjects without at least one dose in the 6 days prior to the dose at the Week 12 visit in the induction study will be considered to take a 0 for the dose for the purposes of assessing an increase from MNT baseline
 - **5-ASA**
 - Rule
 - After first dose and up to and including Week 48: any increase from MNT baseline for more than 5 days
 - After Week 48: Any dose above MNT baseline for greater than 1 day
 - MNT baseline
 - Subjects who have at least one dose in the 6 days prior to the dose of study medication at the Week 12 visit in the induction study will be considered to have a MNT baseline dose >0 . The MNT baseline dose to be used for these subjects is the median nonmissing daily dose from these 6 days. Subjects without at least one dose in the 6 days prior to the dose at the Week 12 visit in the induction study will be considered to take a 0 for the dose for the purposes of assessing an increase from MNT baseline
 - Note

- Subjects cannot start the study on the combination of Beclometasone and mesalazine so there would be no switching. It would be only according to the rules.
 - **Other small molecule immunodulatory active agents**
 - Rule
 - Any exposure after first dose
 - **Leukocyte apheresis, other apheresis, and plasma exchange**
 - Rule
 - Any exposure after first dose
 - **Systemic glucocorticoids**
 - **Systemic glucocorticoids given via oral or rectal routes of administration**
 - Rule
 - After first dose and up to and including Week 48: any increase from MNT baseline for more than 7 days
 - After Week 48: Any dose above MNT baseline for greater than 1 day
 -
 - Equivalency
 - Because of multiple types of systemic glucocorticoids that could be given to the same subject, we need to apply systemic glucocorticoid equivalency rules. Below is the table to follow.
 - MNT baseline
 - Subjects who have at least one dose in the 6 days prior to the dose of study medication at the Week 12 visit in the induction study will be considered to have a baseline dose >0. The MNT baseline dose to be used for these subjects is the median nonmissing daily dose from these 6 days. Subjects without at least one dose in the 6 days prior to the dose at the Week 12 visit in the induction study will be considered to take a 0 for the dose for the purposes of assessing an increase from MNT baseline
 - **Systemic glucocorticoids given via parenteral routes of administration**
 - Rule
 - Any exposure after first dose
 - **Topical glucocorticoids**
 - **Budesonide**
 - Rule
 - Subjects not taking Budesonide at MNT baseline:

in the induction study will be considered to take a 0 for the dose for the purposes of assessing an increase from MNT baseline

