#### **4.5.1 Subject Withdrawal Criteria**

Additional reasons a subject may be withdrawn from study treatment include but are not limited to:

- Adverse events
- Serious AEs
- Meeting the criteria for treatment failure
- Pregnancy
- Protocol deviations
- Failure to return for visits.

A subject should be withdrawn from study treatment:

- If a new therapy is initiated for UC, or
- If a subject undergoes surgery for UC.

Subjects who withdraw from study treatment due to an increase in disease symptoms may see nonstudy-related physicians for treatment and may receive treatments prohibited during the treatment periods of this study.

If a subject chooses to withdraw from study participation due to personal concerns related to a pandemic (eg, coronavirus disease [COVID-19]) or other future similar unexpected public health concerns requiring physical distancing that may result in subjects missing their visits (other than a COVID-19-related or other pandemic-related AE), this should be specified as the reason for subject withdrawal in the source document.

If a subject withdraws their consent, no further evaluation should be performed, and no additional data should be collected. The sponsor may retain and continue to use any data collected before such withdrawal of consent.

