### 5.2.2 Prohibited Treatment

The following common treatments are excluded medications for this study. As the subjects are transferred from induction studies SHP647-301 or SHP647-302, during which these treatments were also prohibited, no washout period is applicable.

- Anti-integrin or antiadhesion molecule treatment (eg, natalizumab, vedolizumab, efalizumab, etrolizumab)
- Parenteral and rectally administered glucocorticoids
- Rectally administered 5-ASA
- Anti-TNF treatment and other biologics with immunomodulatory properties
- Live (attenuated) vaccines
- Any nonbiologic treatment with immunomodulatory properties (other than their current background UC treatment)
- Leukocyte apheresis or selective lymphocyte, monocyte, or granulocyte apheresis or plasma exchange.

Treatments not listed in this section may be considered allowable; see Section 5.2.1 for further details.

No new nonpharmacological therapies that might affect bowel habit or GI function should be started during the study.

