### 5.2.3 Rescue Therapy

Subjects must maintain their stable dose of background UC treatment, unless dose reduction or discontinuation are required due to associated AEs. If a subject requires initiation of a new therapy or increase in glucocorticoids for UC above the SHP647-303 baseline level, the subject should be withdrawn from study treatment and enter the safety follow-up period, and appropriate treatment should be given at the discretion of the investigator.

Subjects who enter the follow-up period will no longer need to abstain from the medications that were prohibited during the baseline and treatment periods. High-dose glucocorticoids and other UC treatments will be allowed. Biologics or nonbiologic immunosuppressants should not be initiated during the safety follow-up period without prior discussion with the sponsor study physician or designee due to the long half-life of ontamalimab.

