**Table 8 Power to Detect the Corresponding Treatment Effect for Key Secondary Endpoints**

Key Secondary Endpoint at Week 52	SHP647 Premise	Placebo Premise	Power (alpha = .05)	Power (alpha = .001)
Endoscopic remission	42.5%	15%	0.99	0.97
Clinical remission	60%	32%	0.99	0.92
Maintenance of remission a	65%	25%	0.96	0.68
Clinical response by composite score	50%	25%	0.98	0.84
Mucosal healing	30%	13%	0.91	0.53
Glucocorticoid-free clinical remission b	50%	19%	0.98	0.79
Glucocorticoid-free remission b	45%	14%	0.99	0.84

a Based on an anticipated 32% of subjects who will be in remission at baseline of this study.

b Based on an anticipated 58% of subjects who will be on corticosteroids at baseline of this study.

With the early discontinuation of the study, the planned sample size of 696 subjects will not be attained as the final number of subjects enrolled into this study is 366. Formal statistical testing of the primary and key secondary endpoints will still be conducted despite not reaching the planned sample size and power levels.

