## Treatment

When medically reasonable, treatment decisions should be deferred until an etiology has been determined. When this is not feasible, management of symptoms should be dictated by the clinical situation. **If management requires a prohibited treatment (eg, intravenous glucocorticoids for induction or maintenance studies) the subject should be withdrawn from treatment.**

If treatment has been deferred, once an etiology is determined (eg, *C. difficile*, disease exacerbation, Campylobacter), appropriate treatment should be promptly implemented without waiting for a scheduled visit. If the etiology is determined to be *C. difficile*, treatment guidelines conforming to the current IDSA recommendations for *C. difficile* infection (McDonald et al., 2018) or the recent expert review on *C. difficile* infection in IBD (Khanna et al., 2017) should be consulted.

If *C. difficile* infection was identified, clinical improvement should be noted within about 5 days after the start of treatment. If improvement does not occur, the etiology is most likely an IBD flare secondary to *C. difficile* and treatment failure assessment should proceed per the protocol. Another possible explanation is primary failure of *C. difficile* therapy which is unlikely.

If an infectious etiology other than *C. difficile* is identified, it should be managed as appropriate, with reference to current clinical guidelines (Shane et al., 2017).

If any infectious etiology is determined, the site should contact the medical monitor to make him or her aware of the diagnosis and to discuss treatment and ongoing study participation.

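### SAP 16.5 has no route term for systemic-class glucocorticoids, so a tapered oral entry dose can mask prohibited rectal use that the site does not act on

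*SAP*

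**What the plan says.** **SAP 16.5.** Oral and rectal systemic-class agents share the heading "Systemic glucocorticoids given via oral or rectal routes of administration". The rule is "After first dose and up to and including Week 48: any increase from MNT baseline for more than 7 days"; after Week 48 the allowance shortens to one day. The reference dose comes from the 6 days before dosing at the induction Week 12 visit: "The MNT baseline dose to be used for these subjects is the median nonmissing daily dose from these 6 days". A subject with no dose in those days has a reference of 0. Different systemic agents are converted by equivalence. Nothing in the available text splits the reference by route or lowers it as the subject tapers. Systemic agents given parenterally have their own rule, under which any use after dosing begins is rescue.

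**SAP 2.2 and 6.1.** Treatment failure, rescue as defined in 16.5, and discontinuation are listed as separate routes to nonresponse. Missing Week 52 data also count as nonresponse.

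**Protocol 5.2.1 and 5.2.2.** Oral glucocorticoids are allowed up to 20 mg/day prednisone-equivalent at entry, with a compulsory taper from Day 1. "Parenteral and rectally administered glucocorticoids" appear together as one prohibited item, and were also prohibited during induction.

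**Protocol withdrawal rules.** Section 5.2.3 directs withdrawal from study treatment when a subject "requires initiation of a new therapy or increase in glucocorticoids for UC above the SHP647-303 baseline level". Section 4.5.1 gives "If a new therapy is initiated for UC" as a ground for withdrawal. Appendix 4 adds: "If management requires a prohibited treatment (eg, intravenous glucocorticoids for induction or maintenance studies) the subject should be withdrawn from treatment".

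**The concern.** A fixed entry-dose ceiling suits oral steroid, because Protocol Table 3 and Section 7.3.3.11 let a subject whose taper fails go back up to an earlier oral dose. Nothing similar supports rectal use. In a compliant subject the MNT baseline dose is wholly oral, so once the taper is under way it becomes headroom for a prohibited route.

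The SAP also treats two equally prohibited routes differently. Parenteral use counts at any exposure, while rectal use inherits the oral ceiling. No reason is given.

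At stake is the primary endpoint and the five key secondary endpoints with no glucocorticoid-free condition: endoscopic remission, clinical remission, sustained remission, clinical response and mucosal healing. Rectal bleeding and the endoscopic subscore, which is read on the sigmoidoscopic segment, are two of the three components of remission. That rectal steroid would improve both is a clinical assumption; the documents do not discuss it. The two glucocorticoid-free endpoints require no glucocorticoid for at least 4 weeks before Week 52, so rectal use in that period does count against a subject there.

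**Working it through.** The plan gives no figure for rescue use, so the check applies the rule to cases and then sizes one misclassified subject.

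**1. The rule.** Let B be the MNT baseline dose, O the current oral dose and R the current rectal dose, all in mg/day prednisone-equivalent. Rescue requires a dose above B for more than 7 days up to Week 48, or for more than 1 day afterwards. The SAP does not say whether the dose compared is O + R or R alone, so both are shown.

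| B | O | R | O + R | Scored as rescue? |
|---|---|---|---|---|
| 20 | 0 | 5, 10 or 20 | 5, 10 or 20 | No, whatever the duration (for example 60 days before Week 48, or 28 days after) |
| 20 | 0 | 25 | 25 | Yes, once past the day allowance |
| 20 | 10 | 10 | 20 | No, on either reading |
| 20 | 10 | 15 | 25 | Yes if summed; no if rectal dose is compared alone |
| 0 | 0 | 5 | 5 | Yes, once past the day allowance |

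After a full taper (O = 0), the unscored range is R ≤ B on both readings. After a partial taper it is R ≤ B − O if routes are summed. Subjects with B = 0 are not affected.

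**2. What the ceiling means in drug terms.** Protocol Appendix 3 equates prednisone 5 mg with hydrocortisone 20 mg. A 20 mg/day entry dose therefore gives 20/5 × 20 = 80 mg/day hydrocortisone as the largest unscored rectal dose after a full taper. This assumes the SAP's own equivalency table, absent from the available text, matches Appendix 3.

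**3. Size of one case.** Inputs: 366 enrolled, 696 planned, 592 of them planned from active induction, four arms in the ontamalimab responder set (Protocol synopsis and 9.6). At the planned split, 366 × 592/696 / 4 = 77.8, about 78 per arm. One subject wrongly kept as a remitter moves that arm's crude rate by 1/78 = 1.28 percentage points. The reported difference is stratum-weighted, so its shift would differ somewhat.

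**4. Conditions that must all hold.** The subject has an oral systemic baseline dose above 0 and has tapered; takes prohibited rectal steroid within the ceiling; is not withdrawn; has no confirmed treatment failure; has Week 52 data; and meets remission. The documents give no frequency for this combination.

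**The case against.** **Withdrawal already covers it.** Protocol 4.5.1, 5.2.3 and Appendix 4 all point to withdrawal, and discontinuation is nonresponse. The gap needs two departures by the site, giving the rectal steroid and keeping the subject on treatment, when a return to an earlier oral dose was available. This stands as the reason the effect is small. It does not close the gap, because the protocol says the subject should be withdrawn, which depends on the site. The estimand also lists 16.5 rescue separately from discontinuation.

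**The SAP follows the protocol's own threshold.** The glucocorticoid trigger in Protocol 5.2.3 is an increase above baseline, also without a route split. That is fair for this trigger. The same sentence has a second trigger, starting a new therapy. Whether rectal steroid is new for a subject who used oral steroid at entry is a matter of interpretation; that it is prohibited is not.

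**Silence on route is not pooling.** Each route could be compared with its own 6-day baseline. Rectal baseline would then be 0 and use beyond the day allowance would be scored. This reading is possible but less natural, given one heading, one rule and one baseline definition.

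**The text is incomplete.** One bullet directly under this rule is blank in the available text, and the equivalency table and most of the topical rules are missing. This stands in full: a route condition in that bullet would remove the point. Rectal topical-class agents cannot be judged.

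**Stronger readings a reader might infer.**
- *Table 8 bounds the number affected.* Its footnote, "Based on an anticipated 58% of subjects who will be on corticosteroids at baseline of this study", is an expectation, does not separate systemic from topical steroid, and counts steroid users, not rectal users. It gives no upper bound on cases.
- *The gap favours one treatment.* Direction depends on which arm uses rectal steroid more, which is unknown.
- *SAP 16.4 contradicts 16.5.* Its rectal category for systemic agents concerns history before induction. It shows only that route is recorded and usable.
- *5-ASA has the same gap.* Oral 5-ASA is to stay at a stable dose, so if doses are summed, added rectal 5-ASA already exceeds baseline.

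**Conclusion.** The point holds as a narrow gap in the scoring rule. On the pooled reading, prohibited rectal systemic-class steroid taken after an oral taper is not rescue at any duration while the dose (the total, if routes are summed) stays at or below the entry-dose equivalent. It changes a result only when the site does not withdraw the subject and Week 52 remission, or the relevant key secondary outcome, is still met. Such use would still appear in the medication and deviation listings (SAP 5.5 and 5.8), but the endpoint would not reflect it.

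The effect is probably very small: about 1.3 points on an arm's crude rate per case at about 78 per arm, with direction and frequency unknown. The conclusion rests on the pooled reading, on enrolment at the planned split, and on the blank bullet holding no route condition. It is a cheap improvement, not a threat to the primary analysis.

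**What to change.** In SAP 16.5, compare the rectal systemic-class glucocorticoid dose with the subject's own rectal dose in the 6 days before the Week 12 induction visit, which is 0 in a compliant subject. An oral baseline dose then cannot offset rectal use. Leave the oral rule and the 7-day and 1-day allowances as they are. If the full SAP already carries a route condition under this rule, no change is needed.

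The cost is a sentence of SAP wording and one route condition on concomitant-medication data already collected. SAP 16.4 already uses route for these drugs, and patient care does not change. The downside is that a few subjects may become nonresponders, and rectal courses within the day allowances stay unscored.
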